## 9.0 Procedures Involved:

Immediately at the onset of the project, we will organize the research team, finalize study procedures and data collection instruments, and design study databases. The PIs and Co-Is will share primary responsibilities for organizing key personnel and staff, plan study implementation, establish standard operating procedures per site, and to detail a plan for secure data collection/ transfer.

### 9.1 Overview & Study Design.

We will conduct a 2-arm, patient-randomized controlled trial at two large, diverse transplant centers (Northwestern University; Mayo Clinic). 700 KT recipients within 2 years of KT will be recruited and followed for 2 years (N=700 patients; n=350 per site; n=175 per study arm per site. Targeting both new and existing KT recipients is important, as adherence barriers may be different. As a result, we will aim to recruit patients

Figure 3. Study Design

with a wide spectrum of time since transplant, ranging from 5 weeks to 2 years post-transplant. In-person interviews will be conducted at baseline and 12 or 18 months (see **Figure 3**). To determine proximal effects of the TAKE IT strategy, a telephone interview will also be administered 6 weeks post-baseline. Follow-up telephone interviews will be conducted at 6, (12 or 18) and 24 months. Electronic health records will be ascertained to capture medication adherence measures and clinical outcomes (**Aim 1**). We will closely evaluate the implementation of all components of the TAKE IT strategy from launch through 2 years (**Aim 2**). Our evaluation includes several process outcomes to assess intervention reliability and sustainability (**Aim 3**). These findings will determine whether modifications to TAKE IT are necessary. Finally, we will further estimate the incremental costs of implementing and sustaining the TAKE IT strategy from the perspective of two transplant centers (**Aim 4**).

Research activities over the 5-year period will be divided into three phases: I) **Preparation** (Months 1-4); II) **Implementation** (Months 5-58), III) **Evaluation** (Months 13-60). In Phase I we will assemble our research team, orient sites, finalize study materials, and pilot test the TAKE IT strategy to ensure it is acceptable to patients, families, transplant clinicians and staff - making any necessary modifications. A randomized controlled trial will then be conducted and participants tracked for 2 years (Phase II). Our evaluation includes summative, process, and cost analyses to fully understand the clinical impact, feasibility, and costs of the TAKE IT strategy to guide dissemination efforts (Phase III).

**9.2 Research Coordinator Training.** A RC at each site will contact participants, engage in the consent process, conduct interviews, perform retention activities, follow-up with patients and perform quality assurance. [name] will oversee project management, ensuring all research staff complete human subjects training (CITI); receive intensive interviewer training, led by Drs. [name] and [name], as well as for safe data transfer. Training will highlight the sensitive nature of assessments. Simulations will monitor interviewer proficiencies.

**9.3 Computer Programming.** We will be using RedCap to collect all data. This allows for straightforward electronic entry of participant responses by the RC and generation of data files compatible with statistical programs. The database is both encrypted and password protected, and is only accessible by approved study personnel at Northwestern. [name] (analyst) will oversee the database structure and quality assurance activities.

**9.4 Data Safety and Monitoring Board (DSMB).** The DSMB will be formed early in the project and be given responsibility to review and approve the methods and analysis plan. It will be organized by Drs. [name] and [name] and include appropriate research methodologists and biostatisticians with related expertise. Meetings will be via video/teleconference to review protocols, procedures, and concerns related to research integrity.

**9.5 Trial Registration.** We will register the trial protocol at ClinicalTrials.gov.

**9.6 Implementation and de-bugging of Monthly Adherence Assessment and Care Alert Notifications.** Due to changes to the hospital and ambulatory care practice electronic

## 9.9 Research Procedures

Research activities will include a baseline interview, and follow-up interviews at 6 weeks, 6 months, 12 months, 18 months and 24 months. The baseline and either the 12 month or the 18 month interview will be conducted in-person\*, while the remaining interviews will be conducted via phone. To facilitate the geographical diversity of KT patients at the Mayo Clinic, measures used in the baseline and 12 month interview can be administered in-person or via phone. If a pill count needs to be completed over the phone, a pill count tray will be sent to the participant prior to the scheduled interview.

\*If the 12-month interview cannot be done in person due to the timing of clinic visits, it will be done over the phone and we will attempt to do the 18 month interview in person.

**Pilot Testing and Refinement of Study Procedures.** We will pilot test our strategy and study protocol, including the evaluation battery and patient materials, among 10 KT recipients per site who meet established patient eligibility criteria. Cognitive interviews (~45 min.) will be conducted to finalize and/or refine all study materials. We will 1) obtain average completion times for the interview, 2) elicit patient comprehension of the interview and intervention components. Necessary modifications will be made prior to full-scale implementation.

**Baseline Interview.** After confirming eligibility via phone, the RC will attempt to schedule the baseline interview to occur in person following an existing outpatient follow-up visit. RCs will review the Transplant Clinic Schedule in Epic to confirm upcoming appointments with the patients. At the baseline interview, the RC will re-introduce the study and obtain written consent, before administering the baseline interview. If a clinic visit is not scheduled, we will schedule interviews at the convenience of participants as necessary. Following the baseline interview, RCs will introduce the ‘Transplant Hero’ mobile application to participants with a smartphone. First, the RC will explain the app and its functionality in reminding patients to take their medications and provide educational information on KT medications. The RC will provide participants with the Transplant Hero Information Sheet. The RC will then ask the participant if they are interested in using the app as part of the study, and confirm that they have a smartphone (previously identified in initial screener and approach). If the participant is interested in downloading the app, the RC will assist in downloading the app. The RC will demonstrate entering a medication into the app, but will not enter the participant’s entire regimen.

As part of a supplementary study leveraging TAKE IT patients (STU00209386), patients will be informed that they may be approached by a research coordinator from the Comprehensive Transplant Center during their upcoming blood draw and will have the option to consent to an additional blood draw. Participants will be informed that they can refuse to participate in the blood draw, without affecting their participation in the TAKE IT study. If the patient is interested in speaking with the IRB-approved coordinator, the patient’s name, date of KT, study ID, and MRN will be shared with the study coordinator using a secured sharepoint platform stored on the FSM drive.

**Follow-up Interviews.** At Northwestern, an automatic reminder function built into Microsoft Access will alert RAs when to schedule follow-up encounters (6 weeks, 6, 12, 18, and 24 month interviews). Northwestern will send Mayo a weekly list of ID numbers and dates, prioritizing patients to schedule based on their windows. Each interview will take approximately 45-60 minutes, and subjects will receive \$30 for baseline, 6 month and 12 month interviews, and \$50 for the 18 month interview (total \$140 compensation; none for 6 week or 24 month 20 minute phone interview).

### **9.10 Intervention: TAKE IT Strategy.**

Our strategy is a multifaceted intervention that leverages the existing resources of a transplant center and increasingly available provider and patient-facing technologies to

simplify KT recipients' role in managing complex, multi-drug regimens and monitor use over time. The goal of the TAKE IT strategy is to optimize adherence and to detect problems earlier in order to improve health outcomes – both in transplant-specific conditions and for comorbidities. This approach is multifaceted, yet highly scalable due to minimal costs and impact on existing transplant center workflow. It includes the following 4 components:

1. **A routine adherence assessment** that requests patients to periodically report upon their medication use, providing a continuous link between the transplant center and patient beyond routine in-person visits. This assessment will routinely identify patients at risk of non-adherence and categorize the nature of their adherence concern in one of the following areas: cognitive, psychological, regimen, medical, social, economic.
2. **Care Alert Notifications** directed to the transplant center nurse coordinator if an adherence related problem is identified by the routine adherence assessment, who can then activate appropriate staff to respond.
3. **Quarterly adherence reports** that will automatically calculate a coefficient of variance for patients' tacrolimus levels at routine intervals and impart results to transplant nurse coordinators.
4. **Tailored clinical support** leveraging transplant center tools to directly target the adherence-related concern identified by the routine adherence assessment. The study team will focus on leveraging existing transplant center resources, including clinical consultation with pharmacists, social workers and transplant nurse coordinators, as well as existing technological and educational tools. These tools will be bundled and initiated in response to specific patient-reported adherence concerns.

### 9.11 Study Arms

Participants will be randomly assigned to either the TAKE IT strategy, as described in section 9.10 or usual care. Usual care refers to the normal standard clinical practices in place at either site, immediately post-transplant to the 5 years following. Northwestern and Mayo follow similar protocols for follow-up. KT recipients at both sites have lab values taken 3 times/weekly for the first 8-10 weeks post-transplant, shifting to weekly lab values for the next 3-4 months after, then monthly labs after. Both sites follow a similar tapering of weekly, to monthly to annual visits to the transplant nephrologist over the first 3 years. Protocol biopsies at both sites are taken between 3-6 months post-transplantation, at 12 then 24 months. All sites have a transplant nurse coordinator who has primary oversight of post-transplant care, full-time pharmacists and a clinical social worker. At Northwestern, the pharmacist has a standard visit with patients to review their prescribed regimen at discharge from the hospital. Social work and pharmacist visits are referrals as needed (PRN). At Mayo, both the pharmacist and social worker engage with patients only upon referral. Neither site has an active portal that engages KT recipients for any self-care support service.

**9.12 Data Sources.** Data sources for this study will include two in-person interviews and four phone interviews with participants, and Electronic Health Record chart review.

**9.13 COVID-19 Survey.**

From a pool of existing studies conducted by [name] (LitCog (STU00026255), REMinD (STU00203777), COPD Multimorbidity (STU00201640), UMS Portal (STU00201639), and TAKE IT (STU00204465), participants will be contacted and invited to participate in a one-time brief (5-10 minute) telephone survey to capture one additional outcome pertaining to their knowledge, attitudes, and beliefs about the COVID-19 outbreak in March 2020. They will also be asked a series of patient-reported health literacy items. Participants who complete to COVID-19 survey will receive a \$10 gift card in the mail.

Recruitment will be done by phone by trained Northwestern RAs. We will contact anyone who has indicated that they were willing to be contacted for future studies run by [name] on the consent form. Verbal consent will be obtained prior to completing the one time brief (5-10 minute) telephone survey.

Data from the COVID-19 survey and patient-reported health literacy items will be captured in REDCap.

**10.0 Data and Specimen Banking:**

**10.1** Upon completion of all study activities, a final de-identified dataset will be created. This dataset will be stored indefinitely on the GIM server for secondary analyses. Only authorized personnel will have access to the dataset.

**11.0 Data and Specimen Management:**

**11.1 Analysis Plan.**

All analyses will be performed in SAS v9.4 (SAS Institute, Cary, NC). [name] will perform analyses under the direct supervision of Drs. [name], [name] and [name]. Drs. [name] and [name] will also provide guidance.

Aim 1.

The proposed trial uses a 1:1 randomized design that assigns patients to TAKE IT or usual care within each cohort. We will accrue approximately 700 patients (350 de novo, 350 established) anticipating 90% retention in the de novo cohort (85% established) for follow-up at 1 year, leaving a minimum 525 patients for primary analyses. High retention will be supported through close follow-up, mailed reminders, birthday cards, and a newsletter. Given the clinical follow-up necessary for KT recipients, we are confident we will achieve this goal.

Regimen adherence at one year is the primary outcome of interest for Aim 1, with Rx knowledge and individual adherence measures also of primary interest. Secondary outcomes include quality of life (PROMIS outcomes and FKSI) and the clinical outcomes of change in eGFR, and any transplant-related re-hospitalization. Blood pressure control in those taking anti-hypertensive medications will also be examined. Relationships between

adherence and potential confounders (age, comorbidity, cognitive ability, regimen complexity, internet use, dose of intervention, etc.) will also be examined. For all outcomes, we will use generalized linear models (GLMs), adjusted for confounders and study site, specifying the logit link function for binary outcomes and identity link for continuous outcomes (quality of life, change in eGFR, SBP). Treatment group will be the independent variable of primary interest, with usual care specified as reference group. We will also include time since transplant at baseline (in months), baseline value of the outcome, and any potential confounding covariates noted in bivariate analysis. For outcomes measured per medication, a generalized estimating equation (GEE) approach will be employed to adjust standard errors for within-patient correlation. Should TAKE IT have an effect on outcomes, secondary analyses will examine if any of the potential confounders considered exhibit any effect modification.

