*Power Calculation.* The sample size calculation was based on the availability of 700 transplant patients estimated by the number of transplants conducted in 2012-2014 across the two sites. With the sample size set at 610 accounting for 85-90% retention at 1 year, we present the minimum differences we will be able to detect between the intervention and usual care arms for each outcome of interest. For the main outcome of medication adherence, we estimate 45% of the sample to be non-adherent using the composite score described above taking estimates for each individual measure into account. We will have sufficient power ( $\geq 80\%$ ) to detect differences of 11% in the entire sample assuming a 5% Type I error rate. Should TAKE IT be associated with potential confounders, calculations show that an R-squared of 0.2 between predictors (a conservatively high estimate under randomization), we would still maintain 70% power to detect the 11% difference. Although adjusting for confounders would decrease variability in adherence, and increase power. Detectable differences for individual adherence measures along with estimates and effect sizes for other outcomes of interest are listed in Table 5.

Table 5. Detectable Differences in Health Outcomes between Study Arms at 1 Year

Outcome	Total (n=610) 305/arm		De Novo (n=270) 135/arm		Established (n=340) 170/arm	
	Usual Care Estimate	Minimum Difference	Usual Care Estimate	Minimum Difference	Usual Care Estimate	Minimum Difference
Primary Outcomes						
Rx Knowledge, %	50	11.3	60	15.9	45	15.1
Rx Non-adherence, %	45	11.0	35	15.2	50	15.0
Self-report, %	35	10.3	29	14.1	44	14.6
Objective (pill count), %	45	11.1	35	11.3	50	15.0
Claims (PDC), %	30	9.8	23	12.7	38	14.0
Biologic (SD Tacrolimus), %	40	10.8	30	14.3	45	14.7
Secondary Outcomes						
Quality of life, mean(SD)	46.2 (9.0)	2.0	45.8 (7.2)	2.5	49.5 (9.0)	2.7
Clinical outcomes						
$\Delta$ eGFR, mean(SD)*	-5.8 (9.0)	2.9	-3.0 (11.0)	3.8	-8.0 (15.0)	4.6
Re-hospitalizations, %	40	10.8	32	14.6	47	14.8
Systolic BP, mean(SD)**	136.7 (8.3)	2.2	138.3 (12.9)	5.1	135.0 (7.9)	2.8

\* $\Delta$  eGFR estimates over 2 years

[figure not shown]
\*\*estimate 75% of cohort has hypertension (Total: n=458, 229/arm; De Novo: n=202, 101/arm; Established: n=256, 128/arm)

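### The stated minimum of 525 analysable patients does not follow from the plan's own accrual and retention (about 612); Table 5's cohort sizes, two of its cells and the 600 in Section 24.4 also conflict with stated inputs

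*Combined protocol and SAP*

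**What the plan says.** Section 11.1, Aim 1, gives the accrual and retention: "We will accrue approximately 700 patients (350 de novo, 350 established) anticipating 90% retention in the de novo cohort (85% established"). The same sentence ends "leaving a minimum 525 patients for primary analyses".

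The Power Calculation paragraph of Section 11.1 uses a different number for the same 1-year analysis: "With the sample size set at 610 accounting for 85-90% retention at 1 year". From a usual-care non-adherence rate of 45%, it claims at least 80% power "to detect differences of 11% in the entire sample assuming a 5% Type I error rate". With an R-squared of 0.2 between predictors, it says "we would still maintain 70% power to detect the 11% difference".

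Table 5 divides the 610 into "De Novo (n=270) 135/arm" and "Established (n=340) 170/arm", and lists a detectable difference for each outcome in the total sample and in each cohort.

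Sections 9.1, 9.7 and 23.1 plan 700 participants, 350 per site. Section 24.4 describes the study data, with interviews from baseline to 24 months, as coming from 600 patients.

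**The concern.** Four sets of figures that should agree do not.

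- The 525 for the primary analyses is not the product of the accrual and retention in its own sentence, and it is not the number used for power.
- Table 5's cohort sizes do not match the cohort accrual in the Aim 1 text.
- Two Table 5 cells print a detectable difference that differs from another row with identical inputs.
- The number of patients in Section 24.4 differs from the number to be enrolled.

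A reader cannot tell whether about 610 or 525 patients are expected in the primary analysis, so a shortfall cannot be judged against the plan. If 525 were the true expectation, the stated 80% and 70% power would not hold. The cohort sizes matter because Aim 2 fits separate models to the two cohorts. The pill-count cell belongs to a measure listed under primary outcomes, and its error makes the trial look more sensitive than it is.

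**Working it through.** **Step 1. Reproduce the headline power.** Inputs from the power paragraph and Table 5: usual care 45%, intervention 34%, 305 per arm, 5% type I error. Sidedness is not stated; two-sided reproduces the table. With pooled variance under the null,

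power = Φ{(d − 1.96 × √(2p̄q̄/n)) / √((p₁q₁ + p₂q₂)/n)}.

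Here p̄ = 0.395, 2p̄q̄ = 0.478 and p₁q₁ + p₂q₂ = 0.472. At n = 305 this is Φ{(0.110 − 0.0776)/0.0393} = Φ(0.824) = 79.5%. An R-squared of 0.2 reduces the effective n to 0.8 × 305 = 244 and gives 70.2%. Both match the plan to rounding.

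**Step 2. The number analysable at 1 year.** From the Aim 1 text:

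- 350 × 0.90 + 350 × 0.85 = 315 + 297.5 = 612.5
- lower rate for everyone: 700 × 0.85 = 595
- 525/700 = 0.75, a retention stated nowhere
- 300 × 0.90 + 300 × 0.85 = 270 + 255 = 525, a 600-patient design, also stated nowhere

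The 610 agrees with 612.5 to within rounding; the 525 does not. The consequences, by the formula in Step 1:

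| Analysed | Per arm | Power, 45% vs 34% | With R² = 0.2 | Detectable from 45% (points) |
|---|---|---|---|---|
| 612 | 306 | 79.6% | 70.3% | 11.05 |
| 610 | 305 | 79.5% | 70.2% | 11.07 |
| 595 | 297.5 | 78.5% | 69.1% | 11.20 |
| 525 | 262.5 | 73.3% | 63.6% | 11.90 |

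**Step 3. The cohort split.** Table 5: 270/0.90 = 300 and 340/0.85 = 400. The Aim 1 text gives 315 and 297.5. To reach Table 5 from 350 and 350, retention would have to be 270/350 = 77% de novo and 340/350 = 97% established, against the stated 90% and 85%. If 350/350 is the plan, the composite non-adherence differences at 1 year become:

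- de novo, 35%, 157.5 per arm: 14.1 points (printed 15.2)
- established, 50%, 148.75 per arm: 16.0 points (printed 15.0, which then has 74.7% power)

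**Step 4. Table 5 cell by cell.** Solving the proportion formula for d at 80% power (knowledge as an increase, all others as a decrease) reproduces 20 of the 21 percentage cells to within 0.1 point. For means, d = (1.96 + 0.84) × SD × √(2/n) reproduces 8 of 9 cells to rounding. The two exceptions are:

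- *Pill count, de novo* (35%, 135 per arm): computed 15.15, printed 11.3. The "Rx Non-adherence" row has the same 35% and 135 per arm and prints 15.2. At 35% versus 23.7% the power is 53%; 80% would need about 254 per arm. Continuity-corrected, one-sided and upward versions range from 13.6 to 17.6, so none gives 11.3.
- *Change in eGFR, Total* (SD 9.0, 305 per arm): 2.80 × 9.0 × √(2/305) = 2.04, printed 2.9. The quality-of-life row has the same SD and n and prints 2.0. A difference of 2.9 (2.85 to 2.95 before rounding) implies an SD of 12.6 to 13.0. The cohort SDs in that row are 11.0 and 15.0.

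**Step 5. The 600.** It equals neither the 700 enrolled (Sections 9.1, 9.7, 23.1) nor the 610 analysed at 1 year. Section 24.4 counts from the baseline interview, so the comparable figure is the number enrolled.

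**The case against.** The strongest reply is that the plan calls 525 a minimum, and an expected 612 does not contradict a lower floor. The sample size was set by the availability of 700 patients, and the power paragraph never uses 525. This stands in part: the power loss at 525 is conditional and does not damage the headline calculation. It does not rescue the sentence, which presents 525 as what is left after the stated retention and names no further loss.

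On the cohorts, both splits total 700 and leave about 610, so the whole-sample analysis is unaffected. The separate cohort models belong to Aim 2 and use repeated measures, whereas Table 5 is for a single 1-year comparison. That is correct: the cohort figures above are not the power of the Aim 2 models. Two incompatible cohort sizes still cannot both be the plan.

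On eGFR, the outcome is secondary, and at an SD of 9.0 the printed 2.9 has about 98% power, so the cell understates sensitivity. The Total inputs may also come from separate sources: the Total quality-of-life mean is 46.2, while the cohorts weighted by size give (270 × 45.8 + 340 × 49.5)/610 = 47.9. The comparison with the cohort SDs is therefore only suggestive. The contradiction with the quality-of-life row does not depend on it.

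The 600 sits in the confidentiality section and drives no calculation. It could be a rounded 610, but the passage covers all interviews from baseline. Alone it would be clerical.

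**Conclusion.** The concern holds in all four parts. The stated inputs give about 612 analysable patients, not 525. Table 5's cohorts imply accrual of 300 and 400, not 350 and 350. The de novo pill-count cell understates its detectable difference by 15.2 − 11.3 = 3.9 points. The Total eGFR SD and difference cannot both be right; the documents do not show which is wrong. The 600 conflicts with 700 enrolled.

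Headline whole-sample power is unaffected if about 610 patients are analysed. Only if 525 is a deliberate floor does it fall to 73% (64% with R-squared 0.2), with a detectable difference of 11.9 points. Apart from pill count, the cohort columns are right only if 300/400 is the plan. These results assume a two-sided 5% test, 1:1 allocation and no continuity correction, the settings under which 28 of the 30 Table 5 cells reproduce. The origin of 525 is not documented; both routes to it in the working are inference. The point should be fixed, but it does not threaten the design.

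**What to change.** - **Aim 1 text:** replace 525 with about 610 to 612. If 525 is a deliberate floor, say so, give its retention assumption (75% of 700), and restate power there as 73% (64% with R-squared 0.2; detectable difference 11.9 points).
- **Cohort split:** either state 300 de novo and 400 established as the planned accrual, or keep 350/350 and recompute both Table 5 cohort columns at about 315 and 297.
- **Pill count, de novo:** correct to 15.2, or to 14.1 if 350/350 is kept.
- **Change in eGFR, Total:** check the SD against its source and make the SD and the difference agree.
- **Section 24.4:** reconcile the 600 with the 700 enrolled, not with the 1-year analysable number.

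The cost is a correction to text and table. It needs no extra patients and no change to design, analysis or conduct.

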#### **24.4 Data Collected.**

The proposed research will include data from 600 patients. Participants will be interviewed at baseline, 6 weeks, 6 months, 12 months, 18 months, and 24 months at Northwestern University and Mayo Clinic. The final data set will include patient socio-demographic characteristics, health status, health literacy and motivation, medication knowledge and

adherence behaviors, as well as clinical outcomes (change in eGFR, re-hospitalization, acute rejection from biopsy, etc.). The primary outcome is medication adherence at year 1. Any identifying information (e.g. personal and/or contact information) will be kept separate from other data; all information will be kept in secure, password protected files.

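### The plan names one lead outcome but labels six as primary with no multiplicity rule; if any one of the six could support a primary claim, the two-sided familywise error would be up to 26.5%.

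*Combined protocol and SAP*

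**What the plan says.** Four places bear on which outcome is primary.

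- Section 11.1, Aim 1: adherence to the regimen at one year is named as the primary outcome, "with Rx knowledge and individual adherence measures also of primary interest". One outcome leads, and others are given primary standing in the same sentence.
- Section 11.1, power calculation: "For the main outcome of medication adherence, we estimate 45% of the sample to be non-adherent using the composite score". This is the only place that ties the lead outcome to the composite. The error rate is given here, as power of at least 80% "to detect differences of 11% in the entire sample assuming a 5% Type I error rate".
- Table 5: the block headed "Primary Outcomes" has six rows: Rx knowledge, Rx non-adherence, self-report, pill count, PDC and tacrolimus SD. A separate block holds the secondary outcomes.
- Section 24.4: "The primary outcome is medication adherence at year 1". The composite is not mentioned.

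Section 1.1 makes knowledge (H1) and medication use (H2) separate hypotheses, and describes medication use through self-report, pill count and tacrolimus levels. Section 8.4 builds the composite as one factor score from the individual adherence measures. No section gives a testing order, a split of the error rate, an adjustment, or a rule for what counts as success across the six.

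**The concern.** Table 5 separates primary from secondary outcomes and puts six in the first group. With no rule linking them, a report could present a significant result on any of the six as a primary finding without contradicting the plan's own labels. The word adherence adds to this: five of the six rows are adherence measures, and Sections 11.1 (Aim 1) and 24.4 do not say which of them is the primary one. At stake is whether a positive primary result carries the 5% error rate that the power section quotes, or a larger one that nobody has stated.

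**Working it through.** **Inputs from the plan.** 1:1 allocation, 610 analysed (305 per arm), 5% type I error, at least 80% power, and the total-sample column of Table 5. Sidedness is not stated.

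**Step 1: reproduce the plan's figure.** For two proportions with pooled variance under the null and no continuity correction,

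power = Φ{[d − z·√(2p̄(1−p̄)/n)] / √([p₁(1−p₁) + p₂(1−p₂)]/n)}.

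Composite: p₁ = 0.45, p₂ = 0.34, d = 0.11, p̄ = 0.395, n = 305, z = 1.96.

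- Null standard error: √(2 × 0.395 × 0.605 / 305) = 0.0396.
- Alternative standard error: √((0.2475 + 0.2244) / 305) = 0.0393.
- Power: Φ[(0.11 − 1.96 × 0.0396) / 0.0393] = Φ(0.82) = 79.5%.
- Exactly 80% power needs 309 per arm, against 305 stated. The figure reproduces.

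The same calculation for all six rows, with the difference taken as a decrease from usual care:

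| Row | Usual care % | Difference | Power, two-sided 5% |
|---|---|---|---|
| Rx knowledge | 50 | 11.3 | 80.4% |
| Composite non-adherence | 45 | 11.0 | 79.5% |
| Self-report | 35 | 10.3 | 79.5% |
| Pill count | 45 | 11.1 | 80.2% |
| PDC | 30 | 9.8 | 79.9% |
| Tacrolimus SD | 40 | 10.8 | 80.2% |

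A one-sided 5% test would give about 87–88%. A two-sided test at 0.05/6 would give about 56–57%. So each row was sized at an unadjusted two-sided 5%.

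**Step 2: familywise error if any one of the six could support a claim.**

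- Independent tests, either direction: 1 − 0.95⁶ = 26.5%.
- Independent tests, favouring TAKE IT only: 1 − 0.975⁶ = 14.1%.

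The plan gives no correlations, so the other values are assumptions. Simulating six equally correlated z-tests (500,000 draws) gives:

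| Common correlation | Either direction | Favouring TAKE IT |
|---|---|---|
| 0 | 26.5% | 14% |
| 0.3 | 24.2% | 12% |
| 0.5 | 20.7% | 10% |
| 0.7 | 16.4% | 8% |
| 0.9 | 10.7% | 5% |

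The nominal rate is 5% in the middle column and 2.5% in the last.

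**Step 3: a structure closer to the plan.** Take the composite as the mean of four equally correlated measures, with knowledge nearly separate. The either-direction figure is then 24.5% when the measures are uncorrelated and 17.1% when they correlate at 0.7.

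**Step 4: what each remedy does to the sample size.** If the composite alone is confirmatory, or is tested first, its error rate is 5% and Step 1 stands unchanged. If all six stay co-equal under Bonferroni (0.05/6 = 0.0083), three things follow.

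- Power for the 11-point composite difference falls from 79.5% to 55.6%.
- The detectable difference rises from about 11.1 to 13.7 points.
- 80% power for 11 points needs 477 per arm: 954 analysed, or 954 ÷ (610/700) ≈ 1,095 enrolled.

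**The case against.** The strongest reply is that the plan already has one primary outcome. The sentence in Section 11.1 opens by naming it, the power section calls it the main outcome and bases its narrative on the composite, and Section 24.4 repeats a single primary. The 5% is attached to that outcome and is not claimed for a set. A reader might infer from Table 5 that the trial's chance of a false primary success simply is 16% to 27%. The documents do not support that. They contain no rule that any of the six is enough, the lower end rests on an assumed correlation of 0.7, and the range counts harmful as well as beneficial results.

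The choice of family can also be argued. Knowledge and medication use are separate hypotheses in Section 1.1, and the four individual measures may be meant as components of the non-adherence row.

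All of that limits the size of the point. It does not remove it.

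- Section 11.1 gives the other outcomes primary standing in words, whatever the layout of Table 5.
- Only the power section links the lead outcome to the composite, while Section 1.1 describes medication use through individual measures. Naming adherence as primary therefore does not settle on one test.
- Controlling error within H2 alone still leaves five adherence rows: 1 − 0.95⁵ = 22.6% if independent, and about 15% at an assumed correlation of 0.7.
- Counting benefit only roughly halves the figures, but it halves the nominal rate too.

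**Conclusion.** The concern holds in conditional form. The plan names one lead outcome, labels five others primary as well, sizes each at an unadjusted 5%, and gives no order or multiplicity rule.

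If the composite alone is confirmatory, the error rate is 5% and nothing is inflated. If a significant result on any of the six could support a primary claim, the two-sided familywise error is at most 26.5% under non-negative correlation. It is about 16% at a correlation of 0.7 and 11% at 0.9. For results favouring TAKE IT the figures are about 14%, 8% and 5%, against 2.5%.

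The sizing is well established, since all six rows reproduce. The amount of inflation is less certain: it depends on correlations the plan does not give and on a success rule it does not state. The two-sided test is inferred from the reproduced figures. The gap should be closed, because as written the plan does not say which of these error rates applies.

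**What to change.** - In Sections 11.1 and 24.4, state that the composite adherence measure at one year is the only confirmatory primary outcome, tested at two-sided 5%. Say which form of it is tested: Table 5 sizes it as a percentage non-adherent, while Section 8.4 describes a factor score and gives no cut-off for it.
- Move Rx knowledge and the four individual adherence measures to secondary. Test them only if the composite is significant, either in a fixed order or by Holm. With five outcomes, Holm requires the smallest p-value to be at most 0.05/5 = 0.01.
- Retitle and regroup the primary block of Table 5 to match.

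This is a change of wording only and should be made before anyone sees outcome data by arm. The 610 analysed patients still serve the composite as the plan calculates. The cost is that knowledge and the individual measures face a stricter threshold, or are reported without a confirmatory claim. Keeping six co-equal primaries under Bonferroni would instead need about 1,095 enrolled, against the 700 planned.
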